10.4.12 Hemoglobin Increase from Baseline ≥ 1.0 g/dL Response Based on Rolling Method

The hemoglobin response will be measured using the consecutive “rolling” 12-week and 24-week time intervals within the entire study period up to the efficacy cutoff, i.e., Days 2 to 85, Day 3 to 86 for 12-week (or Day 2 to 169, Day 3 to 170 for 24-week) and so on. Note that, Day 1 hemoglobin belongs to baseline. The hemoglobin response is defined as subjects with ≥ 1.0 g/dL increase in mean from baseline during any consecutive rolling 12-week (or 24-week) time interval in the absence of transfusion. The Hb values within 21 days following a transfusion may be influenced by the transfusion and will be excluded from this analysis.

The treatment comparison with “rolling” method (luspatercept versus placebo) will be conducted by the CMH test stratified by the randomization stratification factors. The OR (luspatercept versus placebo) with corresponding 2-sided (at 0.05 alpha level) 95% CI and p-value will be provided. The number and percentage of responders will be summarized by each treatment group and the difference in proportions (luspatercept – placebo) and corresponding 95% CI will also be calculated by exact unconditional test with “rolling” method as well.

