3.1.2. Double-blind Treatment Period

Subjects will enter the Double-blind Treatment Period (DBTP) once they have completed the required assessments in the Screening Period and been randomized via the IRT system, as detailed in [Section 7.3](#). The DBTP will begin on Dose 1 Day 1 and will end when all subjects have completed 48 weeks of treatment or have discontinued earlier. At that time, the study will be unblinded.

Subject randomization will occur via the IRT system and Dose 1 Day 1 should be scheduled within 3 days of randomization (can be on the same day as randomization).

Eligible subjects will be randomized at a ratio of 2:1, luspatercept versus placebo, at a starting dose level of 1.0 mg/kg administered by subcutaneous (SC) injection once every 3 weeks. The maximum total dose per administration is 120 mg.

Best supportive care is allowed in both the luspatercept and placebo groups. This will include RBC transfusions, iron-chelating agents, use of antibiotic therapy, antiviral and antifungal therapy, nutritional support as needed, and other medications that are not prohibited (see Section 8.2), thus minimizing the safety risk to patients. Please, also refer to Section 8.1.2 for concomitant medication for anemia, Section 8.1.3 for concomitant iron chelation therapy use and Section 8.1.4 for concomitant RBC transfusions.

Study visits and serial measurements of safety and efficacy parameters will be performed as described in Table 3, Table of Events.

After the study is unblinded, and after DMC's recommendation:

- Subjects who received placebo and have been assessed as per protocol at least up to 48 weeks after the first dose of IP (even if the IP is discontinued before complete 48 weeks of treatment), may access the Open Label Period (OLP) to receive luspatercept for a maximum 15 months before moving to the rollover protocol for longer treatment.
- Subjects receiving luspatercept may continue their treatment in the OLP for maximum 15 months before moving to the rollover protocol for longer treatment (ie, 5 years from Dose 1 in the DBTP, or until treatment discontinuation, whichever occurs later).
- Subjects who received luspatercept and discontinued the IP in the DBTP may continue and/or complete the PTFP of 5 years from first dose of IP, or 3 years from last dose (whichever occurs later), to complete the Post-treatment Follow-up Period under the rollover protocol in this study until the of End of Trial (see Section 3.3).

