 - c. Average of all Hb measurements in Weeks 14-25 (Day 93 to Day 176) if Weeks 14-25 has ≥ 3 Hb measurements
 - d. When the number of Hb measurements is less than 3 among Weeks 13-24, Weeks 12-23, and Weeks 14-25, then choose the largest number of Hb measurements in the following order as Hb at Week 13-24:
 - 1) Hb in Week 13-24
 - 2) Hb in Week 12-23

- 3) Hb in Week 14-25
 - e. Otherwise, missing
 - Weeks 37 - 48 interval: Same rule as Week 13-24 interval
- The calculation of weekly NTDT-PRO scores is detailed in Section 18.3.1. The 12-week interval score is obtained by averaging all the weekly scores (at least one non-missing) in these 12 weeks. If all the weekly scores in these 12 weeks are missing, the 12-week interval score is then declared missing.

This SAP addresses efficacy and safety endpoints during the double-blinded treatment period (including the initial 48-week treatment period for all subjects and the long-term treatment period for early enrolled subjects). The database will be locked upon all subjects completed 48 weeks of the double-blind treatment period or discontinued before reaching 48 weeks. All the data collected up to data cutoff date will be used for summary. Data selection rules will be applied in each summary panel as needed, please refer to individual part for details.

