9.2 Number of Doses Received per Subject

Total number of doses received per subject is defined as the total number of doses the subject received (i.e., total number of non-zero doses). It will be summarized descriptively and categorically (1, 2, 3, 4, 5, 6, 7, 8, 9 – 16, 17 – 24, 25 – 32, >32) by treatment group and total. The total number of doses received will be calculated from all subjects within each treatment group. The total number and percentage of doses received for each planned dose level (1.25 mg/kg, 1.0 mg/kg, 0.80 mg/kg, 0.60 mg/kg, 0.45 mg/kg) will be calculated within treatment group, with the total number of doses received as denominator.

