10 EFFICACY ANALYSIS

All efficacy evaluations will be conducted using the ITT population with the exception of FACIT-F Fatigue Subscale (SF) and SF-36 analyses that will be conducted on the HRQoL evaluable population. NTDT-PRO T/W and SoB scores will be analyzed by both ITT and HRQoL populations. The primary and key secondary endpoints will also be analyzed based on the Per Protocol population as a sensitivity analysis.

Some continuous variables like hemoglobin and weekly NTDT-PRO T/W and SoB domains will be derived as the sum of results over 12 weeks divided by the number of assessments. The mean over 12 weeks will be used to derive mean change from baseline for each subject.

For the early treatment-discontinued subjects, i.e. subjects who did not complete 24 weeks or 48 weeks of double-blinded treatment period, the transfusion and assessment records (including Hb and QoL) will still be collected up to 48 weeks post Dose 1 Day 1 or 9 weeks post last dose, whichever is the later date. All the assessments before the efficacy cutoff date will be used to evaluate primary and secondary endpoints. For these endpoints, if at the time of data summary, a subject has died or has not reached the end of the 12-week interval, this subject will be included in the analysis. For other efficacy endpoints, the collected records will be used (by visits or at specified time point) as needed, depending on the purpose of the summary. Please refer to the individual endpoint section for details.

The efficacy cutoff date is defined as the minimum date among death date, study discontinuation date, last dose date + 20, and data cutoff date. For the primary and responder-related secondary endpoints, if at the time of data summary, a subject's efficacy cutoff date is before the end of the 12-week interval or a subject has any invalid hemoglobin records (i.e., within 21 days following a transfusion) during the specified 12-week interval, this subject will be included in the analysis and his/her responder status will be classified in accordance with the definition of erythroid response in Section 10.2. For other efficacy endpoints, if a subject's efficacy cutoff date is before the end of the 12-week interval, the subject will be included in the analyses.

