Statistical comparisons will be made between luspatercept and placebo. Key secondary efficacy results that will be considered statistically significant after consideration of the strategy for controlling the family-wise Type 1 error rate are described in Section 10.1. All statistical tests will be 2-sided at the significance level of $\alpha = 0.05$, and the corresponding p-values and 2-sided CIs for point estimates will be reported, unless specified otherwise.

In general, descriptive statistics will be provided and statistical tests will be applied if appropriate. For continuous variables, least squares (LS) means with corresponding standard errors (SE) for each treatment group, along with LS mean of treatment difference (luspatercept versus placebo) with corresponding 95% CI and p-value will be presented for analysis of covariance (ANCOVA). Counts and percentages will be used to describe categorical variables, and the treatment comparison will be analyzed analogous to the primary efficacy endpoint, using the CMH model

stratified by baseline randomization stratification factor(s). The odds ratio (OR) (luspatercept versus placebo) with corresponding 2-sided (at 0.05 alpha level) 95% CI and p-value will be provided. The difference in proportions (luspatercept – placebo) and 95% CI will also be calculated. A forest plot showing the ORs, 95% CI and p-value for the overall result and the results in each subgroup will be constructed for primary and key secondary endpoints. For all endpoints mentioned in this section, records beyond week 48 will not be used unless otherwise specified. If ANCOVA is used, the statistical assumption will be validated first, log transformation will be applied as needed.

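### The rolling Hb response in SAP 10.4.12 has no common time horizon, so its reported rate rises with time on treatment even without a drug effect; a minor point in a supportive analysis

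*SAP*

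**What the plan says.** SAP 10.4.12 shifts 12-week and 24-week windows one day at a time from Day 2 and searches "time intervals within the entire study period up to the efficacy cutoff". A subject responds if mean Hb is at least 1.0 g/dL above baseline in "any consecutive rolling 12-week (or 24-week) time interval in the absence of transfusion". The arms are compared with a CMH test stratified by the randomization factors only, with an odds ratio, a p-value, and an exact interval for the difference in proportions.

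The cutoff comes from SAP Section 10: "The efficacy cutoff date is defined as the minimum date among death date, study discontinuation date, last dose date + 20, and data cutoff date". It contains no Week 48 term. The same section has a general rule that "records beyond week 48 will not be used unless otherwise specified".

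Follow-up differs by design. Under Protocol 3.1.2 the double-blind period "will end when all subjects have completed 48 weeks of treatment or have discontinued earlier", which is a single calendar end for everyone. SAP 5.1 accordingly covers double-blind data "including the initial 48-week treatment period for all subjects and the long-term treatment period for early enrolled subjects". The dose-count categories in SAP 9.2 run to more than 32 doses, and 32 doses at 3-week intervals is 96 weeks.

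**The concern.** A maximum over more windows cannot be smaller than a maximum over fewer. A subject who responds by one horizon also responds by every later one, so time on treatment feeds directly into the response rate. Two consequences follow.

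First, the reported proportion has no defined time frame. It depends on how early subjects enrolled and how long they stayed on treatment, and it cannot be read beside the fixed Weeks 13-24 and Weeks 37-48 rates.

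Second, a plain CMH test on ever-responder status treats ascertainment time as equal. Because last dose + 20 days ends the search, any difference between arms in treatment stopping passes into the comparison. Neighbouring sections deal with unequal follow-up: SAP 10.4.13 censors duration at the cutoff, and SAP 10.4.11 uses fixed Weeks 1-24 and 1-48. Section 10.4.12 does neither.

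**Working it through.** **Inputs from the documents.** Window rule, cutoff and Week 48 default as above; 100 versus 50 subjects, 50% versus 10% response, two-sided alpha 0.05, 10% dropout (SAP 4.4); Weeks 13-24 = Day 86 to Day 169 (SAP 5.1). **Assumed, because the documents do not give them:** within-subject SD and autocorrelation of Hb, and treatment stopping by arm.

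**The plan's own figure.** No figure is stated for the rolling analysis. The 10% placebo rate used below comes from the sample-size section, whose power reproduces. The pooled rate is (50 + 5)/150 = 0.367. The null SE is sqrt(0.367 × 0.633 × (1/100 + 1/50)) = 0.0835, and the alternative SE is sqrt(0.25/100 + 0.09/50) = 0.0656. Then (0.40 − 1.96 × 0.0835)/0.0656 = 3.60, a power of 99.98%. With 90 versus 45 subjects it is 99.95%. The plan states at least 99%.

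**Which horizon applies.** The Section 10 default yields wherever a section specifies otherwise. Section 10.4.12 does so, and 10.4.13 defines the entire study duration as running from Day 2 to the efficacy cutoff.

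**Number of 12-week windows.** The first window is Days 2-85, so D − 84 windows end on or before Day D.

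| Week | Day | Windows |
|---|---|---|
| 24 | 169 | 85 |
| 48 | 337 | 253 |
| 72 | 505 | 421 |
| 96 | 673 | 589 |

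**Chance response rate.** Simulation of 40,000 subjects with no drug effect: stationary AR(1) Hb every 3 weeks, baseline the mean of two screening values, no transfusions, weekly autocorrelation 0, 0.7, 0.9 or 0.97. The within-subject SD was set to give the stated fixed Weeks 13-24 rate (0.65-0.90 g/dL for 10%, 0.51-0.70 for 5%, 0.41-0.56 for 2%). The ranges are over autocorrelation.

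| Fixed-window rate | Week 24 | Week 48 | Week 72 | Week 96 |
|---|---|---|---|---|
| 10% | 10-17% | 24-28% | 32-34% | 37-40% |
| 5% | 5-9% | 14-17% | 20-22% | 23-28% |
| 2% | 2-4% | 7-8% | 9-13% | 11-18% |

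A second model (Ornstein-Uhlenbeck drift, time constants 12 and 30 weeks, measurement SD 0.35, fixed-window rate about 10%) gives 12-13%, 26-27%, 34-35% and 39-42%. Only the 12-week windows were simulated.

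**Arm comparison with no drug effect.** An arm's rate is the sum over horizons of (share followed to that horizon) × (chance rate there). Take the 10% case with autocorrelation 0.9, where the rates at Weeks 24, 48, 72 and 96 are 0.123, 0.245, 0.321 and 0.373.

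- Luspatercept, assumed shares 5/25/35/35%: 0.006 + 0.061 + 0.112 + 0.131 = 31.0%.
- Placebo, assumed shares 20/25/28/27%: 0.025 + 0.061 + 0.090 + 0.101 = 27.6%. Difference 3.4 points.
- With a Week 48 limit: 0.05 × 0.123 + 0.95 × 0.245 = 23.9%, against 0.20 × 0.123 + 0.80 × 0.245 = 22.1%. Difference 1.8 points.

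Two other assumed patterns, with follow-up capped between Weeks 48 and 100:

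| Stopping by Week 48, placebo vs luspatercept | To efficacy cutoff | Week 48 limit |
|---|---|---|
| 25% vs 10% | 3.5-4.2 points | 2.3-2.5 points |
| 40% vs 15% | 6-7.5 points | 3.8-4.6 points |

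The limit removes about 35-40% of the null difference in these two patterns and just under half in the worked example.

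**Null rejection rate at nominal 5%, search to the efficacy cutoff.** With equal follow-up it is 5.0-5.5%. With 5% (luspatercept) versus 20% (placebo) stopping by Week 24 it is 5-7%. With 5% versus 35% it is 8-14%.

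**Scale.** At a rate near 30% the SE of the difference is sqrt(0.21 × 0.03) = 7.9 points. The limit removes 1.2-1.7 points in the first tabulated pattern and 2.2-2.9 in the second, about 0.15 to 0.4 SE.

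**The case against.** The strongest reply is that little depends on this analysis. Rolling response does not appear in the readable endpoint lists of Protocol Table 2 or SAP 4.2, and it lies outside the gatekeeping of SAP 10.1. Protocol 9.6.3.12 uses rolling windows only for duration and plans no test between groups there. The primary and key secondary Hb endpoints use fixed windows. All of this stands, and it is why the point is minor.

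A reader might infer that the test is invalid or that the luspatercept effect will be inflated. The documents do not support that. Randomization balances enrolment date, and with equal follow-up the type I error stays near 5%. Bias needs stopping that differs by arm, but SAP 4.4 assumes one 10% dropout rate with no split by arm. The stopping patterns above are assumptions. If luspatercept subjects stopped sooner, the bias would run the other way.

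It can also be said that the Week 48 default already governs. The wording of 10.4.12 points against this. If Week 48 was intended, two programmers could still derive different responder sets, and the same sentence settles it.

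Finally, a Week 48 limit leaves more than half of any stopping-driven difference in the patterns tried. That is correct, and the limit should not be presented as a cure.

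**Conclusion.** The point holds as a minor one. As written, the rolling response rate has no fixed horizon and rises with time on treatment without any drug effect. The direction is certain because adding windows can only add responders. The size is conditional: about 26% at Week 48 and about 40% at Week 96 if the fixed-window rate is 10% and arises wholly from random variation, but only 7-8% and 11-18% if that rate is 2%. These figures rest on an assumed SD and autocorrelation, Hb every 3 weeks and no transfusions.

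The arm comparison is affected only under differential stopping. In the patterns tried, the null difference stays below one standard error of the comparison. Nothing here touches the primary or key secondary results.

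**What to change.** In SAP 10.4.12, base the response rates, CMH test, odds ratio and CI for the difference on windows ending on or before Day 337. This is Week 48 on the SAP's own count (24 × 7 + 1 = 169; 48 × 7 + 1 = 337) and matches the Section 10 default. Show later windows descriptively by time on treatment.

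State that this reduces but does not remove the shortfall for subjects who stop before Week 48. Add a sensitivity analysis that searches every ITT subject to Day 337, setting aside the last dose + 20 days term and using the post-discontinuation Hb already collected up to Week 48. Those visits are sparse (Weeks 13, 19, 24, 37, 42 and 48, plus 9 weeks after last dose), and 10.4.12 sets no minimum number of Hb values per window, so the text should state one.

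Note that SAP 10.4.13 and 10.4.17 still apply the rolling method to the efficacy cutoff, so their responder counts may differ from the tested set.

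The cost is a short SAP edit, one derivation filter and one extra table, with no new data. Rolling rates become lower in both arms, possibly by several points. In the worked example above they fall from 31.0% to 23.9% and from 27.6% to 22.1%.

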10.4.13 Duration of Mean Hemoglobin Increase from Baseline ≥ 1.0 g/dL

To measure the duration of hemoglobin response (for the ≥ 1.0 g/dL criterion), both the 12-week and 24-week rolling methods mentioned from Section 10.4.12 will be applied.

The duration of the longest continuous 12-week (or 24-week) based hemoglobin response will start from the first day of the first rolling 12-week (or 24-week) interval that achieves mean Hb increase from baseline ≥ 1.0 g/dL with the exclusion of hemoglobin assessments within 21 days after transfusion. It will end with the last day of the last consecutive rolling 12-week (or 24-week) interval that maintains mean Hb increase from baseline ≥ 1.0 g/dL.

The Kaplan-Meier plots of duration of mean hemoglobin increase from baseline ≥ 1.0 g/dL over rolling 12-week (or 24-week) time interval, defined as time from the start of the longest response to end of the response, will be provided. The median duration, 25th and 75th quartiles with the associated 2-sided (at 0.05 alpha level) 95% CIs will be presented for each treatment group. Descriptive statistics will also be generated for the duration for each treatment group.

The duration of the individual continuous response is defined as the number of days between the First and Last Days of Response, i.e. Last Day of Response – First Day of Response + 1, where the First Day of Response is the first day of the first 12-week interval when the subject meets response requirement, and the Last Day of Response is the last day of the last 12-week (or 24-week) interval when the subject meets response requirement. The subject must meet the response requirement on all the days within the entire duration.

For subjects who have one response and continue to respond at the efficacy cutoff date, the end day of the response will be censored at the date of efficacy cutoff and the duration of response will be calculated as date of efficacy cutoff – first day of response + 1, where date of efficacy cutoff is defined in Section 10. For subjects who have multiple responses and their last responses continue on the efficacy cutoff date, the longest response will be the last one if the duration from the response start to censoring is longer than all the previously occurred response durations. If the continuing response duration is not the longest compared with the previously occurring responses, the response with the longest duration will be selected. Summary statistics will be provided for the total duration of hemoglobin response within the entire study period and the ratio of the total response duration versus entire study duration. The entire study duration is defined as period from Day 2 to date of efficacy cutoff.

10.4.14 6MWT: Mean Change at Week 24 and 48

For 6MWT assessments, mean changes from baseline at Weeks 24 and 48 will be summarized descriptively and analyzed using ANCOVA method with treatment group, randomization stratification factor(s) and baseline 6MWT value as the covariates. In addition, subgroups of subjects with baseline 6MWT ≤ 450 meters and > 450 meters will be performed. Other subgroup analyses will be added as described in Section 10.5.

Mean changes from baseline at Week 48 will be analyzed similarly.

10.4.15 Proportion of Mean Hemoglobin Increase from Baseline ≥ 1.5 g/dL at Week 13 to 24

Similar to the primary efficacy analysis, the proportion of subjects who have an increase from baseline ≥ 1.5 g/dL in mean of hemoglobin values over a continuous 12-week interval from Week 13 to Week 24 in the absence of transfusions will be performed on the ITT population. The Hb values within 21 days following a transfusion may be influenced by the transfusion and will be excluded from this analysis. Cochran-Mantel-Haenszel (CMH) test will be performed with treatment group and randomization stratification factor(s) in the model to compare the treatment and placebo groups at 2-sided 0.05 level.

10.4.16 Proportion of subjects with a decrease from baseline \geq (RD) in mean NTDT-PRO T/W score, over Weeks 13 to 24 and Weeks 37 to 48

The responder definition (RD) threshold is the individual subject score change over a predetermined time period that will be interpreted as a treatment benefit. The RD threshold of 1 for the NTDT-PRO is jointly determined by longitudinal anchor based and distribution-based methods prior to database lock using data collected over a 12-week window between Weeks 13 to 24 ([REDACTED]).

Proportion of subjects with a decrease from baseline \geq RD (=1) in mean NTDT-PRO T/W score, over Weeks 13 to 24 and Weeks 37 to 48 in the luspatercept group will be compared with the placebo group. The CMH test will be used with baseline NTDT-PRO T/W category ≥ 3 versus <3 as the stratum to compare the response rates between the 2 groups. The corresponding 95% confidence interval for odds ratio will also be provided.

The cumulative distribution function (CDF) of observed changes in NTDT-PRO T/W over a continuous period of Weeks 13 to 24 and Weeks 37 to 48 from baseline will be generated by treatment group. The CDF curve presents the entire distribution of responses and shows a continuous plot of the entire range of changes from baseline at a given post-baseline visit on the x-axis and the cumulative percentage of subjects experiencing a change up to a particular level on the y-axis.

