	Proportion of subjects with improvement of iron overload at Week 24 and Week 48, as measured by: 
 ○ For subjects with baseline liver iron concentration (LIC) (by magnetic resonance imaging [MRI]) ≥ 3 mg/g dw: $\geq 20\%$ reduction in LIC, OR $\geq 33\%$ decrease in iron chelation therapy (ICT) daily dose ○ For subjects with baseline LIC (by MRI) < 3 mg/g dw: no increase in LIC > 1 mg/g dw AND not starting treatment with ICT or no increase in ICT daily dose $\geq 33\%$, if on ICT at baseline 	Baseline ICT dose is based on medical history over 24 weeks prior to randomization; ICT drug and dose collected at every visit	X	X

Table 2: Study Endpoints (Continued)

Endpoint	Name	Description	Endpoint Measurement	
			Wk 24	Wk 48
Secondary Efficacy Endpoints	Mean change from baseline in serum ferritin at Week 24, Week 48 and up to last assessment	All values available in the medical history over 24 weeks prior to randomization will be entered in the Electronic case report form (eCRF)	X	X
	Mean change from baseline in LIC at Week 24, Week 48 and up to last assessment	LIC at screening, Week 24, 48 and in the OLP, as applicable	X	X
	Proportion of subjects who are transfusion-free over 24 weeks	Occurrence of transfusions is assessed at every visit	X	
	Proportion of subjects who are transfusion-free over 48 weeks	See description above		X
	Duration of the mean hemoglobin increase from baseline ≥ 1.0 g/dL	Time from first to last Hb measurement with increase from baseline ≥ 1.0 g/dL	X	X
	Mean change from baseline in the 6-minute walk test (6MWT) distance at Week 24 and Week 48	6MWT is performed every 4 doses, eg, Dose 1, 5, 9, etc. and at Week 24 & Week 48 (± 7 days) regardless of dose delay and even if the IP is discontinued	X	X
	Proportion of subjects who have an increase from baseline ≥ 1.5 g/dL in mean of hemoglobin values over a continuous 12-week interval from Week 13 to Week 24 in the absence of transfusions	See description above for baseline Hb	X	
	Proportion of subjects with a decrease from baseline \geq RD in mean NTDT-PRO T/W score, over Weeks 13 to 24 and Weeks 37 to 48	NTDT-PRO is administered as a daily diary for 24 weeks and after that over the 7 days prior to receiving IP dose	X	X

Table 2: Study Endpoints (Continued)

Endpoint	Name	Description	Endpoint Measurement	
			Wk 24	Wk 48

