9.6.3.12. Duration of Mean Hemoglobin Increase from Baseline ≥ 1.0 g/dL

Descriptive statistics will be generated for the duration of mean hemoglobin increase for each treatment group. Kaplan-Meier method will be used for censored subjects. No statistical test will be performed to compare the 2 groups.

The duration will start from the first day of the first rolling 12-week window that achieves mean Hb increase from baseline ≥ 1.0 g/dL. It will end with the last day of the last consecutive rolling 12-week window that maintains mean Hb increase from baseline ≥ 1.0 g/dL.

9.6.3.13. 6MWT: Mean Change at Week 24 and 48

Mean changes from baseline at Weeks 24 and 48 will be analyzed using ANCOVA method with treatment group and randomization stratification factor(s) in the model and baseline 6MWT value as the covariate. In addition, subgroup of subjects with baseline 6MWT ≤ 450 meter will be performed.

Mean changes from baseline at Week 48 will be analyzed similarly.

9.6.3.14. Proportion of Mean Hemoglobin Increase From Baseline ≥ 1.5 g/dL at Week 13 to 24

Similar to the primary efficacy analysis, the proportion of subjects who have an increase from baseline ≥ 1.5 g/dL in mean of hemoglobin values over a continuous 12-week interval from Week 13 to Week 24 will be performed on the ITT population. Cochran-Mantel-Haenszel (CMH) test will be performed with randomization stratification factor(s) in the model to compare the treatment and placebo groups at 2-sided 0.05 level.

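### SAP 10.4.13 runs the duration-of-response Kaplan-Meier analysis on each subject's longest Hb response, Protocol 9.6.3.12 defines duration on the first, and Protocol Table 2 gives a third definition

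*SAP*

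**What the plan says.** Three places define this endpoint.

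- **Protocol 9.6.3.12.** On the start: "The duration will start from the first day of the first rolling 12-week window that achieves mean Hb increase from baseline" by at least 1.0 g/dL. On the end: "It will end with the last day of the last consecutive rolling 12-week window that maintains mean Hb increase from baseline" by the same amount. Kaplan-Meier is to be used for censored subjects, and the groups are not to be tested against each other.
- **SAP 10.4.13.** The Kaplan-Meier variable is "defined as time from the start of the longest response to end of the response". For a single response still running, "the end day of the response will be censored at the date of efficacy cutoff". With several responses, a running last response is used if it is already the longest. Otherwise: "If the continuing response duration is not the longest compared with the previously occurring responses, the response with the longest duration will be selected". Median and quartiles with 95% confidence intervals are reported by group, for 12-week and 24-week windows. Total response duration and its ratio to study duration are also summarised.
- **Protocol Section 2, Table 2.** The description column reads "Time from first to last Hb measurement with increase from baseline" of at least 1.0 g/dL. It uses no rolling window.

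Duration of erythroid response is a stated secondary objective in both documents (Protocol Table 1, SAP 3.2). The endpoint is listed under other secondary endpoints in SAP 4.2.2.2 and is outside the gate-keeping sequence of SAP 10.1.

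**The concern.** A median duration of response, reported by arm with a confidence interval, is normally read as how long a response lasts before it is lost. Protocol 9.6.3.12 defines that quantity. The SAP takes the maximum over all of a subject's responses, which is a different quantity and one that tends to grow with follow-up, because longer observation gives more chances for a longer run. SAP 5.1 provides for 48 weeks in all subjects and longer treatment in those enrolled early, so follow-up will vary. The SAP gives no reason for the change. A reader who goes from the protocol to the reported median would take it for time to loss of the first response, and it would usually be too long for that.

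**Working it through.** Neither document states an expected duration, event count or median for this endpoint, so there is no figure to reproduce. The check is a comparison of the rules, followed by a simulation for size.

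**Step 1: which response each text selects.** In Protocol 9.6.3.12 the word consecutive ties the end to the run that began at the first qualifying window. The duration therefore stops when that run is broken. SAP 10.4.13 borrows part of this wording ("The duration of the longest continuous 12-week (or 24-week) based hemoglobin response will start from the first day of the first rolling" qualifying interval) but attaches it to the longest response. Its rule for subjects with several responses leaves no doubt that the maximum is meant.

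**Step 2: direction.** Let D1, D2, ... be a subject's successive response durations.

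- Protocol 9.6.3.12: T = D1.
- SAP 10.4.13: T = max(D1, D2, ...), which is at least D1.

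The two differ exactly when some later response is longer than D1. Constructed examples:

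| Responses, in order | Protocol 9.6.3.12 | SAP 10.4.13 |
|---|---|---|
| 120 days ended, 250 days ended | 120 | 250 |
| 100 days ended, 200 days ended, 150 days running at cutoff | 100 | 200 |
| 200 days ended, 150 days running at cutoff | 200 | 200 |

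The third row shows that losing and regaining response is not enough to make the two differ. The Table 2 description would run across the gap between responses and so matches neither column.

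For each subject the SAP duration is never shorter. With censoring, this does not by itself order two Kaplan-Meier curves at every time point. In the scenarios of Step 3, however, the SAP median or quartile was above the first-response value, or equal to it, wherever both were reached.

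**Step 3: size under assumptions.** Taken from the documents: 84-day windows rolling from Day 2 (SAP 10.4.12), the 1.0 g/dL threshold, 21-day dosing visits with Hb measured, and at least 48 weeks (336 days) of follow-up. Assumed, because the documents give no values: mean Hb change 1.0 g/dL, SD 0.7 between and 0.5 within subjects, autocorrelation 0.3, and an upper follow-up limit of 110 weeks (770 days). Records after Week 48 count here because SAP 10.4.12, whose rolling method 10.4.13 adopts, runs to the efficacy cutoff.

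| Quantity | First response | Longest response | Difference |
|---|---|---|---|
| 25th percentile, days | about 146 | about 188 | 188 - 146 = 42 |
| Median, days, follow-up 48-110 weeks | about 272 | about 440 | 440 - 272 = 168 |
| Median, follow-up 48 weeks for all | not reached | not reached | - |

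Between 13% and 26% of responders have a longest response that is not their first. With visits 21 days apart the quantiles move in 21-day steps, so these are approximate.

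**Step 4: sensitivity.** Eighteen further scenarios used mean change 0.7, 1.0 or 1.3 g/dL, between-subject SD 0.6, within-subject SD 0.4 or 0.7, autocorrelation 0.3 or 0.7, and follow-up of 336 or 336-700 days. Of responders, 19-59% had more than one response, but only 9-31% had a longest response that was not the first. Medians, first against longest:

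- 167 v 209 days (mean 0.7, within-subject SD 0.7, autocorrelation 0.3, 336 days)
- 188 v 293 days (mean 1.0, within-subject SD 0.7, autocorrelation 0.3, 336-700 days)
- 230 v 314 days (mean 1.0, within-subject SD 0.7, autocorrelation 0.7, 336-700 days)

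**The case against.** **Limited impact.** The endpoint is descriptive, is not tested between groups and carries no alpha. The SAP labels its variable openly as the longest response and also reports total response duration. Subjects with one response, or whose first is the longest, are unaffected. All of this stands and limits the weight of the point. It does not make the SAP variable the one defined in Protocol 9.6.3.12.

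**The protocol is not uniform.** Table 2 differs from 9.6.3.12, so the SAP cannot be said simply to depart from a single protocol definition. That is right. It means three texts need reconciling. Section 9.6.3.12 is the analysis text and the more specific of the two.

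**The sizes rest on assumptions.** This is also right. With 48 weeks for everyone, the main setting reaches no median under either definition, so the 168-day gap depends on longer follow-up.

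**A stronger reading that a reader might infer.** When the longest response is complete and a shorter one is still running, the SAP gives no censoring for the completed one. A reader might conclude that it is wrongly counted as an event, that the longest-response estimate is biased downward, and that such subjects should be censored. The documents do not support this.

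- The SAP never states the event flag for that case; it has to be inferred.
- In simulation, 64-94% of these subjects had a first response that was also the longest. For them an event is correct under Protocol 9.6.3.12.
- Take as target the longest response begun by the cutoff and followed to its end. The inferred SAP coding stayed close: 25th percentile 188 v 188 days, median 440 v 440. Censoring these subjects overshot: 25th percentile 230 days, median not reached.

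**Conclusion.** The mismatch is real and follows from the text alone. Protocol 9.6.3.12 defines the first unbroken response, SAP 10.4.13 analyses the longest, and Protocol Table 2 describes something else again. A subject's SAP duration can only equal or exceed the 9.6.3.12 duration, so the SAP median and quartiles should not be read as time to loss of first response. The share of responders affected and the shift in quantiles depend on assumed Hb variability and follow-up. The shares seen run from roughly one in eleven (9%) to three in ten (31%), and the median gap from 42 days (209 - 167) to 168 days where medians were reached. The finding concerns the choice of response only. It does not extend to the SAP's event coding for the longest response. Because the endpoint is descriptive and outside the testing sequence, no inferential claim is at risk. What is at risk is the meaning of a reported secondary result.

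**What to change.** - In SAP 10.4.13, make the Kaplan-Meier analysis the duration of the first response as in Protocol 9.6.3.12. Count an event at the end of its last consecutive qualifying window, and censor only if that response is still running at the efficacy cutoff.
- Reconcile the Table 2 description in the protocol with that definition.
- If the longest response is kept, label it a supportive descriptive summary, separate from the protocol's endpoint.
- If the 24-week version is kept, state which response it uses.

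The cost is SAP wording, a correction to one protocol table entry and reprogramming of one derivation. No new data are needed. The downside is that the reported median will be shorter.
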